7. DISCONTINUATION OF STUDY INTERVENTION AND PARTICIPANT DISCONTINUATION/WITHDRAWAL

7.1. Discontinuation of Study Intervention

It may be necessary for a participant to permanently discontinue study intervention. Reasons for permanent discontinuation of study intervention include the following: AEs; parent(s)/legal guardian or participant request; investigator request; pregnancy; and protocol deviation (including no longer meeting all inclusion criteria or meeting 1 or more exclusion criteria).

Note that discontinuation of study intervention does not represent withdrawal from the study. If study intervention is permanently discontinued, the participant should remain in the study to be evaluated for safety. All participants for whom study intervention was discontinued after the last dose of the primary series or the booster dose will be followed for safety and immunogenicity, as applicable. See the [SoA](#) for data to be collected at the time of discontinuation of study intervention and follow-up for any further evaluations that need to be completed.

In the event of discontinuation of study intervention, it must be documented on the appropriate CRF/in the medical records whether the participant is discontinuing further receipt of study intervention or also from study procedures, postvaccination study follow-up, and/or future collection of additional information.

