8.3. Safety Assessments

Planned time points for all safety assessments are provided in the [SoA](#). Unscheduled safety measurements may be obtained at any time during the study to assess any perceived safety issues.

A clinical assessment, including medical history, will be performed on all participants at their first visit to establish a baseline. Significant medical history will be documented in the CRF.

AEs and SAEs are collected, recorded, and reported as defined in [Section 8.4](#).

Acute reactions within the first 30 minutes after administration of the study intervention will be assessed and documented in the AE CRF.

The safety parameters also include reactogenicity e-diary reports of local reactions, systemic events (including fever), and use of antipyretic medication that occur in the 7 days after administration of the study intervention. These prospectively self-collected occurrences of local reactions and systemic events are graded as described in [Section 8.3.3.1](#).

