8.3.3. Electronic Diary

All participants will report prompted local and systemic events in an e-diary to assess reactogenicity. The participant's parent(s)/legal guardian will be asked to monitor and record local reactions, systemic events, including fever, and antipyretic/pain medication used to treat symptoms, each evening for 7 days following vaccination (Day 1 through Day 7, where Day 1 is the day of vaccination) on a system that uses a PDA or other technology. This system, hereafter referred to as the participant's e-diary, allows recording of these assessments only within a fixed time window, thus providing the accurate representation of the participant's experience at that time. Data on local reactions, systemic events, and antipyretic/pain medication used to treat symptoms reported in the e-diary will be transferred electronically to the e-diary vendor, where they will be available for review by investigators, their qualified designees, and sponsor staff at all times via an internet-based portal. At intervals agreed to by the vendor and Pfizer, these data will be transferred electronically to Pfizer for analysis and reporting. These data do not need to be reported by the investigator in the CRF. However, if a participant withdraws because of prompted reactogenicity events reported in the e-diary, the event(s) should be recorded on the AE page of the CRF, regardless of whether the investigator considers the event(s) to be clinically significant.

Investigators (or an appropriately qualified designee) are required to review the e-diary data online to evaluate participant compliance and as part of the ongoing safety review.

The investigator or designee must contact the participant's parent(s)/legal guardian in order to obtain stop dates for any reactions ongoing on the last day that the e-diary was completed. The stop dates should be documented in the source documents and the information entered in the CRF.

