3.1.1.3. Adverse Events and Serious Adverse Events

Standard algorithms for handling missing AE dates and missing AE severity will be applied as described in the Pfizer vaccine data standard rules. Completely missing AE start dates will not be imputed.

The following derivations (yes/no) will be included for each participant:

- Any AE reported within 30 days (Day 1 through Day 31) after each dose and after any dose
- Any related AE reported within 30 days (Day 1 through Day 31) after each dose and after any dose
- Any immediate AE (AE start time is within 30 minutes after vaccination) reported after each dose and after any dose
- Any severe AE reported within 30 days (Day 1 through Day 31) after any dose
- Any AE leading to study withdrawal after the first dose
- Any AE leading to death after the first dose

AE reports will exclude any reactogenicity events (but not exclude reactogenicity SAEs) reported in the AE CRF during the e-diary collection period.

- Any AESI reported during the study after the first dose

Because this study does not include active surveillance for LD, diagnosis terms under the ICD-10 code for LD (A69.2) that represent clinical diagnoses of acute LD (early, early disseminated, or late manifestations) made by a qualified healthcare provider will be considered AESIs for this study. The AESI PTs will be included in the data handling memo before the database lock.

- NDCMCs reported during the study after the first dose
- SAEs reported during the study after the first dose (including reactogenicity events reported in the AE CRF during the e-diary collection period)
- Related SAEs reported during the study after the first dose (including reactogenicity events reported in the AE CRF during the e-diary collection period)

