6.1.2.1. Main Analysis

- Estimand strategy: Treatment policy ([Section 2.2.1.1](#)).
- Analysis set: Safety population ([Section 4](#)).

- Intercurrent events and missing data: All data collected are included.
- Analysis methodology: Calculation of the 95% CI of the proportion of participants reporting those events will use the Clopper-Pearson method ([Section 5.2.1](#)).
- Descriptive statistics including the proportion (%) and the numerator (n) and the denominator (N) used in the proportion calculation, and 95% CI for percentage using the Clopper-Pearson method, will be presented for each vaccine group. Data will be summarized by age group separately (5 through 11 and 12 through 17 years), as well as for the overall study population.
- The main analysis will be based on AEs and will exclude the reactogenicity events that were reported in the AE CRF (except for SAEs) ([Section 3.1.1.3](#)).

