6.1.2.2. Supplementary Analysis

To support the assessment of AEs, the endpoints below, as specified in Section 3.1.1.3, will be summarized with the same analysis population using the same presentation as specified in the main analysis.

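### The reactogenicity exclusion, as written, also removes nonserious events from the AE-leading-to-withdrawal and immediate-AE tables, and no summary covers AEs that end vaccination

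*SAP*

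**What the plan says.** SAP 3.1.1.3 lists the AE derivations. Two of them matter here: "Any immediate AE (AE start time is within 30 minutes after vaccination) reported after each dose and after any dose" and "Any AE leading to study withdrawal after the first dose". After these and the other AE items (any, related, severe, leading to death) comes the rule "AE reports will exclude any reactogenicity events (but not exclude reactogenicity SAEs) reported in the AE CRF during the e-diary collection period". SAP 6.1.2.1 repeats it: the main AE analysis "will exclude the reactogenicity events that were reported in the AE CRF (except for SAEs"). The supplementary analysis in SAP 6.1.2.2 says only that "the endpoints below, as specified in Section 3.1.1.3, will be summarized with the same analysis population"; no endpoints follow, and nothing is restored.

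SAP 3.1.1 defines which events are affected. They are AEs within 7 days of a dose whose preferred term (PT) the clinical team has flagged as reactogenicity before database lock. These are merged with the e-diary data.

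The protocol says where the events are recorded. E-diary reactogenicity normally does not go on the CRF, but under Protocol 8.3.3 "if a participant withdraws because of prompted reactogenicity events reported in the e-diary, the event(s) should be recorded on the AE page". Protocol 8.3 adds: "Acute reactions within the first 30 minutes after administration of the study intervention will be assessed and documented in the AE CRF".

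On stopping vaccination, Protocol 7.1 states: "Note that discontinuation of study intervention does not represent withdrawal from the study". Protocol 8.4.1 requires an AE that causes discontinuation of study intervention to be recorded on the CRF.

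**The concern.** AEs leading to withdrawal, immediate reactions and AEs that end vaccination are standard tolerability outputs, and this is a pediatric study whose only objective is safety. Protocol 2.3.1 describes the common AEs after VLA15 as mainly reactogenicity, so reactogenicity is a foreseeable reason for a child to withdraw or stop. The protocol takes care to put those cases on the AE page; the SAP rule then takes the nonserious ones out of the tables that would show them. The comparator is saline, so any under-count would be expected mainly in the VLA15 arm. A reader of the AE-leading-to-withdrawal table alone could conclude that no child left because of nonserious reactogenicity, whatever happened.

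**Working it through.** The plan gives no figure for this point, so the check traces records through the stated rules.

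**1. Does the exclusion reach the two derivations?** Its position in SAP 3.1.1.3 and its repetition in 6.1.2.1 say yes. SAEs are the only exception in both places. The SAE and related-SAE items state that they include reactogenicity events; the withdrawal and immediate-AE items carry no such note. SAP 6.5.1 builds its MedDRA summaries from the same categories.

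**2. Are the records the protocol asks for the ones removed?**
- Reactogenicity that causes withdrawal under Protocol 8.3.3 was reported in the e-diary, so it falls on Days 1 to 7. If nonserious and coded to a flagged PT, it is excluded.
- An immediate AE starts within 30 minutes, so it is always on Day 1. Whether it stays depends only on seriousness and on whether its PT is flagged.

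The flagged PTs are not listed in the SAP. I assume that the terms for the prompted events will be among them.

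**3. Where one such event is counted** (nonserious, flagged PT, Day 1, participant withdraws):

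| Output | SAP section | Counted? |
|---|---|---|
| Reactogenicity presence, severity, duration, onset day | 3.1.1.1, 3.1.1.2, 6.1.1 | Yes, with no link to withdrawal or to the 30-minute window |
| Immediate AE, if onset is within 30 minutes | 3.1.1.3 | No |
| AE leading to study withdrawal | 3.1.1.3 | No |
| Disposition table and listing of withdrawals | 6.4.2 | Yes, under the reason in the database |

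Disposition gives a general reason; Protocol 7.2 offers both AEs and a parent or participant request. It shows no event term or severity, and it uses the randomized population. The AE tables use the safety population as received. The two can therefore disagree, and the SAP plans no reconciliation.

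**4. Stopping vaccination without leaving the study.** Protocol 7.1 names AEs as a reason for permanent discontinuation, and Protocol 2.3.1 says that participants with significant reactions after the first vaccination will get no further doses. SAP 3.1.1.3 has no matching derivation. SAP 6.4.2 counts who received each dose, but gives reasons only for withdrawal. Nothing links the reaction to the missed doses.

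**5. Size, for illustration only.** Number on VLA15 = total × 3/4.
- Protocol 9.5: 3000 × 0.75 = 2250, as the protocol states.
- SAP 2.3: 3550 × 0.75 = 2662.5, about 2660.

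Participants missing from the withdrawal table = number on VLA15 × assumed rate of withdrawal for nonserious, flagged reactogenicity:

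| Assumed rate | 2250 on VLA15 | 2662.5 on VLA15 |
|---|---|---|
| 0.05% | 1.1 | 1.3 |
| 0.5% | 11.3 | 13.3 |

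**The case against.** A reader might infer that withdrawals caused by reactogenicity will be reported as zero in this study. The documents do not support that. SAP 6.4.2 tabulates withdrawals by dose, reason and vaccine group and lists the participants. Serious reactogenicity, events after Day 7 and unflagged PTs all stay in the AE tables. The excluded events are moved, not lost: they enter the reactogenicity rates, a primary endpoint, at the highest grade from either source. These objections stand, and they confine the point to two AE tables.

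Three further objections have weight.
- Prompted reactions and AEs are separate endpoints in both documents, and using AE CRF events as reactogenicity data follows FDA feedback. Keeping flagged events out of the general AE incidence is therefore defensible and is not challenged here. The feedback as described in the SAP does not mention removing events from withdrawal or immediate-AE outputs.
- The protocol says where to record these events but states no analytic purpose. That the AE-page entry was meant to feed the withdrawal and immediate-AE summaries is an inference.
- The term for AE reports is undefined and the sentence sits between bullets, so its scope is read from position and from 6.1.2.1. A narrower scope may be intended, but nothing in the text says so.

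On stopping vaccination, it would be too strong to say that such an AE is counted nowhere. If flagged and on Days 1 to 7, it counts as reactogenicity; if not flagged and within 30 days, it counts as an AE. Only a summary linking it to discontinuation is absent.

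**Conclusion.** The point holds in limited form. Under the rules as written, nonserious AE CRF events with a flagged PT on Days 1 to 7 contribute zero to the AE-leading-to-withdrawal table and are missing from the immediate-AE table. Both tables under-count, and the first may not match disposition. The absence of any summary of AEs leading to discontinuation of study intervention is a separate, smaller gap.

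The size is unknown. About 1 to 11 VLA15 recipients at N = 2250, or about 1 to 13 with the SAP's larger enrollment, follows from an assumed 0.05% to 0.5%; neither document gives a rate. The conclusion rests on two readings: that the exclusion covers every AE derivation listed before it, and that the PTs of the prompted events will be flagged. The expected direction, mainly affecting VLA15, rests on the saline comparator and on the AE profile in Protocol 2.3.1.

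**What to change.** 1. State in SAP 3.1.1.3 and 6.1.2.1 that the reactogenicity exclusion does not apply to the immediate-AE and AE-leading-to-study-withdrawal derivations, which use all AE CRF records, flagged PTs included. The death derivation needs no change, because an AE leading to death is an SAE and is already kept.
2. Add a derivation of any AE leading to permanent discontinuation of study intervention, on the same basis.
3. Reconcile the AE-leading-to-withdrawal table with the disposition table and explain any remaining differences.

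The cost is SAP wording and a few lines of programming. No new data are needed, since the protocol already requires these events on the CRF. Some events will then appear in both the reactogenicity and the AE tables; a footnote covers that overlap.

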3.2. Secondary Endpoints

No secondary endpoints are defined in this study.

3.3. Other Endpoints

No other endpoints are defined in this study.

3.4. Baseline Variables

Day 1 is defined as the day of the first vaccination dose for the overall study assessment.

Demographic variables to be collected include sex, race, ethnicity, and date of birth. Age at Dose 1 (in years) will be derived based on birthday. Two age groups will be derived: 5 through 11 and 12 through 17 years.

Medical history of clinical significance will be collected and categorized according to the current version (at the time of reporting) of MedDRA.

3.4.1. E-Diary Completion for Each Dose

An e-diary will be considered transmitted if any data for the local reactions and systemic events are present for any day. If all data are missing from all items (local reactions and systemic events) in the e-diary for all 7 days after vaccination, then the e-diary will be considered not transmitted. An e-diary will be considered transmitted for a given day if any data are present for that day. The following variables will be derived:

- e-diary data transmitted on each day (Day 1 through Day 7)
- e-diary data transmitted on any day (Day 1 through Day 7)
- e-diary data transmitted on both Day 1 and Day 2
- e-diary data transmitted from Day 1 through Day 3
- e-diary data transmitted from Day 1 through Day 4
- e-diary data transmitted from Day 1 through Day 5
- e-diary data transmitted from Day 1 through Day 6
- e-diary data transmitted for all 7 days

3.5. Safety Endpoints

3.5.1. Adverse Events

A 3-tier approach will be used to summarize AEs, PTs, and SOC. Under this approach, AEs are classified into 1 of 3 tiers. Different analyses will be performed for different tiers:

- Tier 1 events: These are prespecified events of clinical importance and are maintained in a list in the product's safety surveillance review plan.
- Tier 2 events: These are events that are not Tier 1 but are "relatively common."
A MedDRA PT is defined as a Tier 2 event if it is reported by at least 1% of participants in any vaccine group.
- Tier 3 events: These are AEs that are neither Tier 1 nor Tier 2 events.

4. ANALYSIS SETS (POPULATIONS FOR ANALYSIS)

Data for all participants will be assessed to determine if participants meet the criteria for inclusion in each analysis population prior to unblinding and releasing the database, and classifications will be documented per standard operating procedures.

For purposes of analysis, the following analysis sets are defined in Table 6.

Table 6. Summary of Analysis Sets

Participant Analysis Set	Description
Enrolled/entered	All participants who have a signed ICD.
Randomized population	All participants who are assigned a randomization number in the IRT system.
Safety population	
All enrolled participants who received at least 1 dose of the study intervention.
 
The safety population will be defined below for each dose:
 
• Safety population for Dose 1: The participants who received the first dose of the study intervention (VLA15 or placebo).• Safety population for Dose 2: The participants who received 2 doses of the study intervention.• Safety population for Dose 3: The participants who received 3 doses of the study intervention.• Safety population for Dose 4: The participants who received 4 doses of the study intervention.

Table 6. Summary of Analysis Sets

Participant Analysis Set	Description
E-diary safety population	
All participants who received the study intervention (VLA15 or placebo) and had at least 1 day of reactogenicity data reported through the e-diary or AE CRF.
 
Note: If all participants had at least 1 day of e-diary transmitted, this will be the same as the safety population.
 
The e-diary safety population will be defined below for each dose:
 
• E-diary safety population for Dose 1: The participants who received the first dose of the study intervention (VLA15 or placebo) and had at least 1 day of reactogenicity data reported through the e-diary or AE CRF during the Dose 1 e-diary collection period.• E-diary safety population for Dose 2: The participants who received 2 doses of the study intervention (VLA15 or placebo) and had at least 1 day of reactogenicity data reported through the e-diary or AE CRF during the Dose 2 e-diary collection period.• E-diary safety population for Dose 3: The participants who received 3 doses of the study intervention (VLA15 or placebo) and had at least 1 day of reactogenicity data reported through the e-diary or AE CRF during the Dose 3 e-diary collection period.• E-diary safety population for Dose 4: The participants who received 4 doses of the study intervention (VLA15 or placebo) and had at least 1 day of reactogenicity data reported through the e-diary or AE CRF during the Dose 4 e-diary collection period.

If a participant received a vaccine dose not as randomized, the safety analysis set will be based on the vaccine actually received. Participants are assigned to the VLA15 group if they received at least 1 dose of VLA15; participants are assigned to the placebo group if they received only placebo throughout the study.

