9.3.1. General Considerations

Unless stated otherwise, “vaccine group” in this section refers to participants receiving VLA15 or placebo. CIs for all endpoints in the statistical analysis will be presented as 2-sided at the 95% level unless specified otherwise.

The safety analyses are based on the safety population. Participants will be summarized by vaccine group according to the study interventions they actually received. Missing AE dates will be imputed according to Pfizer safety rules. Completely missing e-diary data (ie, all 7 days of e-diary collection were missing) will not be imputed. For partially complete e-diary data (ie, 1-6 days of reactogenicity data are available), it is assumed that no reactions or events were experienced on missing days based on the e-diary data source.

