2.1. Modifications to the Analysis Plan Described in the Protocol

There are no changes in any analyses from the plan specified in the protocol.

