3. ENDPOINTS AND BASELINE VARIABLES: DEFINITIONS AND CONVENTIONS

3.1. Primary Endpoints

3.1.1. Primary Safety Endpoints

Primary safety endpoints include both reactogenicity data and AEs collected from the e-diary and the AE CRF.

Based on feedback from the FDA on multiple vaccine programs, reactogenicity data will utilize both e-diary data (prompted local reactions and systemic events) and reactogenicity events reported in the AE CRF during the e-diary collection period.

Since the AE CRF does not designate a specific page to collect reactogenicity data for an untransmitted e-diary, Pfizer has adopted a process of providing a listing of AEs reported within 7 days after vaccination for the clinical team to review and determine (“flag”) which PTs should be considered reactogenicity events before the database lock. AEs reported on the same day of vaccination that are missing a start time are defaulted to AEs reported after vaccination. Following these review steps, those AEs reported within 7 days after vaccination that match flagged PTs will be considered reactogenicity data. If the same reactogenicity event is reported on the same day from both the e-diary and the AE CRF, the highest grade from the 2 data sources will be used for that specific day for analysis.

It should be noted that the data collection in the AE CRF is different from that of the e-diary:

- For redness, swelling, and fever, the measured size of redness and swelling at the injection site and temperature are recorded in the e-diary but not in the AE CRF. As the missing e-diary entries are monitored in an ongoing review of the prompted reactions reported in the AE CRF, any measurement recorded in the query response will be considered for the primary analysis, using the data handling memo for analysis purposes. For the 7 days, only the maximum grading from both sources will be used for the aggregated severity analysis.
- For pain at the injection site and all other systemic events, the severity grading algorithm for the e-diary data and the AE CRF may not be the same. Pfizer will choose the highest severity grade.

Any AEs recorded on the AE CRF for 7 days following study intervention administration (Day 1 through Day 7) that are considered local reactions or systemic events will be consolidated with the e-diary data and included in the reactogenicity report.

The subsections below describe how to derive each safety endpoint.

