5.3.1.1. Reactogenicity Data

For the derived variables based on reactogenicity e-diary data, if any day of the 7-day e-diary is available, the “any day (Day 1 through Day 7)” data will be considered as nonmissing.

The reactogenicity data are collected in the e-diary, which does not allow participants to skip any questions. Therefore, for a specific day, if the e-diary data are transferred for that day, all of the reactogenicity data for the participant on that day are nonmissing.

In general, any participant with all 7 days of reactogenicity data missing from the e-diary and AE CRF will not be included in the analysis (ie, assuming MCAR). If only Days 1 through 6 of the 7 days of e-diary data are transferred, it is expected that these reactogenicity events would be queried by the investigator for the missing e-diary days and entered in the AE CRF if any reactogenicity was not reported in the e-diary due to missed days; therefore, the primary analysis will use the reactogenicity recorded in the AE CRF to impute the partially missing e-diary data to estimate the reactogenicity rate during the e-diary collection period. The AE CRF is designed as a log, which means only events that were observed by the participant will be recorded, and events that were not observed will not be recorded. Therefore, after applying the AE CRF data, imputing the remaining e-diary missing days as “no” for the primary analysis is reasonable. However, data for the missing day(s) will not be imputed in the analysis of each specific day.

A sensitivity analysis will be planned for completers. Only participants with all 7 days of e-diary data transferred will be included in this sensitivity analysis.

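### The per-dose e-diary safety population admits a child with no diary only if an event is on the AE CRF, so the denominator of the main reactogenicity rates depends on the outcome

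*SAP*

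**What the plan says.** The main analysis of local reactions and systemic events (SAP 6.1.1.1) uses the e-diary safety population. SAP Section 4, Table 6, defines that set overall and for each dose: the child was dosed and "had at least 1 day of reactogenicity data reported through the e-diary or AE CRF".

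Two passages fix what the AE CRF can contribute. SAP 3.1.1 begins its account with "Since the AE CRF does not designate a specific page to collect reactogenicity data for an untransmitted e-diary", and then provides that "those AEs reported within 7 days after vaccination that match flagged PTs will be considered reactogenicity data". SAP 5.3.1.1 says of the log that "only events that were observed by the participant will be recorded, and events that were not observed will not be recorded".

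SAP 5.3.1.1 treats missing diaries in two ways. For a wholly missing diary, "any participant with all 7 days of reactogenicity data missing from the e-diary and AE CRF will not be included in the analysis", on an MCAR assumption. For a partly missing diary, AE CRF events are used first and the remaining days are set to *no*.

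Protocol 9.3.1 bases safety analyses on the safety population and says "Completely missing e-diary data (ie, all 7 days of e-diary collection were missing) will not be imputed". It mentions no AE CRF route into the reactogenicity analysis. SAP 2.1 states: "There are no changes in any analyses from the plan specified in the protocol". The SAP version history does record the added AE CRF source and attributes it to FDA comments.

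**The concern.** A child with no diary for a dose has no means of entering that dose's set as a *no*. With a flagged AE CRF event, the child joins both numerator and denominator; without one, the child joins neither. Membership of the set is thus decided by the outcome being estimated. An exclusion triggered by having no recorded event also sits badly with an MCAR label.

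The two missing-data rules disagree as well. The log works the same way for every child, yet silence in it means *no* when one diary day exists and *missing* when none does.

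These rates are a primary endpoint, and the estimand (SAP 2.2) covers all participants with at least one dose. No planned table separates the effect of the admission rule from everything else.

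**Working it through.** **Plan figure.** The documents give no figure for this effect, so there is none to reproduce.

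**Inputs.** From the documents: about 2250 VLA15 recipients (Protocol 9.5), hence 750 on placebo at 3:1, and two-sided 95% Clopper-Pearson intervals. SAP 2.3 gives a larger total (3550), but the bias in points does not depend on the total. Assumed, because the documents are silent: *m*, the share of dosed children with no diary day for the dose; *p*, the true rate; *s*, the chance that a no-diary child's reaction reaches the AE CRF.

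**Direction.** If A of B diary children report a reaction and k no-diary children are admitted, all with that reaction, the rate becomes (A + k)/(B + k), which exceeds A/B whenever A < B.

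**Size under MCAR, unreported reactions left missing (SAP Tables 3 and 4).**

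Reported rate = p(1 − m + ms)/(1 − m + mps)

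Bias = msp(1 − p)/(1 − m + mps)

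At m = 5%, s = 0.5, p = 50%: 0.5 × 0.975/0.9625 = 50.65%, a bias of 0.65 points. At m = 20%: 0.5 × 0.90/0.85 = 52.94%, a bias of 2.94 points.

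Bias in percentage points at p = 50%:

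| m | s = 0.25 | s = 0.5 | s = 1 |
|---|---|---|---|
| 1% | 0.06 | 0.13 | 0.25 |
| 5% | 0.33 | 0.65 | 1.28 |
| 10% | 0.68 | 1.35 | 2.63 |
| 20% | 1.52 | 2.94 | 5.56 |

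At p = 10% and m = 5%, the values are 0.12, 0.24 and 0.47. For scale, the Clopper-Pearson half-width at 50% is 2.09 points for n = 2250 and 3.64 for n = 750.

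**In counts** (2250 children, m = 5%, s = 0.5, p = 50%). There are 112.5 children without a diary. About 28.1 are admitted, all with events, and 84.4 are dropped.

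- SAP rule: (1068.75 + 28.125)/(2137.5 + 28.125) = 50.65%.
- Diary-defined denominator: 1068.75/2137.5 = 50.0%.
- All dosed, silence counted as *no*: 1096.875/2250 = 48.75%.
- All dosed, every no-diary child counted as *yes*: (1068.75 + 112.5)/2250 = 52.5%.

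**If unreported reactions are set to *no*.** With c the share of no-diary children admitted on any event, the rate of one reaction is p(1 − m + ms)/(1 − m + mc). At p = 10%, m = 10%, c = 0.3: s = 0.1 gives 0.1 × 0.91/0.93 = 9.78% (−0.22 points), and s = 0.5 gives 0.1 × 0.95/0.93 = 10.22% (+0.22 points).

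**Group difference** (m = 10%, s = 0.5 in both groups). True rates of 50% and 20% become 51.35% and 20.88%, so the difference shifts by +0.47 points. True rates of 90% and 40% become 90.48% and 41.30%, a shift of −0.83 points.

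**Outside MCAR.** With 50% reacting among diary children, 70% among the rest, m = 10% and s = 0.25: (0.45 + 0.0175)/(0.90 + 0.0175) = 50.95%, against a truth of 52.0% for all dosed children, an error of −1.05 points.

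**The case against.** Much of the case on the other side stands.

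- Entry is on any local or systemic event, and the SAP tabulates no composite of the two. A child admitted for headache is not a case of redness. A reader might infer that every tabulated rate is pushed up; that does not follow, because the direction for a single reaction depends on a coding rule the SAP leaves open.
- A reader might extend the point to all any-dose rates. A child with a diary after any one dose is in the any-dose set regardless, so only children with no diary at any dose matter there.
- Upward bias is certain only under MCAR. If children without diaries react more often and capture is low, the net error can be downward.
- One day with any data counts as a transmitted diary (SAP 3.4.1), and sites review diaries online, so non-transmission may be small. The Table 6 note recognizes that the set equals the safety population if everyone transmits at least one day. A claim that the intervals are invalid, or that a false dose trend will appear, would need non-transmission rates that the documents do not give.
- The sensitivity analysis in children with all 7 diary days (SAP 5.3.1.1 and 6.1.1.3) removes every AE-CRF-only child, and SAP 6.4.2 reports diary completion by group. However, the completer analysis also removes all partial diaries and is specified for maximum severity, so it does not isolate this effect.
- Using a recorded AE is not imputation, so the SAP does not breach the protocol's no-imputation sentence. The SAP may modify the plan, and its version history discloses the new source. What remains is that SAP 2.1 is wrong as it stands.
- Merging AE CRF events for diary children only would lose events, because SAP 3.1.1.3 and 6.1.2.1 already exclude nonserious reactogenicity events from the AE tables. Any fix must allow for this.

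None of these points removes the outcome-dependent entry to the per-dose sets.

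**Conclusion.** The per-dose e-diary safety population depends on the outcome, and the SAP reads an empty AE CRF log in two incompatible ways. Under the SAP's own MCAR assumption, and with unreported reactions left missing, per-dose rates of any local or any systemic reaction are biased upward. With those reactions set to *no*, rates can move either way.

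The size cannot be fixed from the documents. At 5% non-transmission or less and capture of 0.5 or less, it stays under about 0.7 points, well inside the VLA15 half-width of 2.09 at a 50% rate. It passes that half-width only when non-transmission and capture are both high, for example 20% with 0.5 or 10% with 1. It is zero if every child transmits at least one diary day for the dose.

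The documents support a defect in the definition of the main analysis set that is worth correcting before database lock. They do not support a claim that the reactogenicity results will be materially wrong.

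**What to change.** 1. For Dose k, base the main rate on participants with at least one e-diary day transmitted for that dose, with their AE CRF events merged. In the same table, give on a separate line the number of non-transmitters and their AE-CRF-only reactogenicity events, so that no event is lost between the reactogenicity and AE tables.
2. Add an analysis on the safety population for Dose k in which a non-transmitter with an AE CRF event counts as *yes* and one without counts as *no*. This matches the rule for partial diaries. It will read low when capture is incomplete (48.75% against 50% in the example), so it should be presented beside the first rate and not in place of it.
3. If the current FDA-prompted set is kept as the main analysis, prespecify items 1 and 2 as sensitivity analyses and state whether an admitted child's unreported reactions are coded *missing* or *no*.
4. Correct SAP 2.1 to declare the added AE CRF source and the changed analysis set relative to Protocol 9.3.1.

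The cost is SAP wording and one extra table set, with no new data. Reported rates would probably be slightly lower.
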